8.4.5 Adverse Event Reporting

The Principal Investigator and designated study team members are responsible for detecting, documenting, and reporting unanticipated problems, adverse events (AEs), including serious adverse events (SAEs), and deviations in accordance with NIH policy, and IRB requirements. Relatedness to the research of all serious adverse events will be determined by the PI in consultation with the CD.

Serious unanticipated problems and serious protocol deviations will be reported to the IRB and CD as soon as possible and in writing not more than 7 days after the PI first learns of the event.

Deaths will be reported to the Clinical Director within 7 days after the PI first learns of the event.

All adverse events, deviations, and unanticipated problems will be summarized and reported at the time of Continuing Review.

Table 2. Adverse events associated with CLN3

Category		Adverse Event
HEENT	Eyes	Low vision/blindness; abnormal movements (nystagmus); photophobia; visual hallucination
	Ears	Auditory hallucination; abnormalities in Behavioral Hearing and ABR tests
	Oromotor/ Speech	Dysphagia; drooling; dysarthria

Cardiovascular		Sinus arrhythmias; prolonged ECG intervals; elevated BNP
Hematology		Decreased serum iron, % saturation
Endocrinology		Abnormal TSH; low vitamin D
Musculoskeletal		Abnormal gait; falls; scoliosis; in-toeing; abnormal muscle tone; tremors
Neurological		Brain atrophy; seizures; cognitive impairment; memory impairment; sleep disruption; fatigue
Psychiatric/Behavioral		Irritability; aggression; perseveration; anxiety; mood instability

ABR: auditory brainstem response. BNP: pro-brain natriuretic peptide. ECG: electrocardiogram. HEENT: head, eyes, ears, nose, throat. TSH: thyroid stimulating hormone

8.4.6 Serious Adverse Event Reporting

The study investigator shall report the event to the reviewing Institutional Review Board (IRB) IC's designee and as soon as possible, but in no event later than 7 calendar days after the investigator first learns of the effect.

8.4.7 Events of Special Interest

Not applicable.

8.4.8 Reporting of Pregnancy

Not applicable.

8.5 UNANTICIPATED PROBLEMS

8.5.1 Definition of Unanticipated Problems (UP)

Any incident, experience, or outcome that meets **all** of the following criteria:

- Unexpected in terms of nature, severity, or frequency given (a) the research procedures that are described in the protocol-related documents, such as the Institutional Review Board (IRB)-approved research protocol and informed consent document; and (b) the characteristics of the participant population being studied; and
- Related or possibly related to participation in the research (“possibly related” means there is a reasonable possibility that the incident, experience, or outcome may have been caused by the procedures involved in the research); and
- Suggests that the research places participants or others (which may include research staff, family members or other individuals not directly participating in the research) at a greater risk of harm (including physical, psychological, economic, or social harm) than was previously known or expected.

8.5.2 Unanticipated Problem Reporting

The investigator will report unanticipated problems (UPs) to the NIH Institutional Review Board (IRB) as per Policy 801.

8.5.3 NIH Intramural IRB Reporting of IND Safety Reports

Not applicable.

9 STATISTICAL CONSIDERATIONS

9.1 STATISTICAL HYPOTHESIS

- Primary Endpoint(s): The primary endpoint of this study is to assess the safety and feasibility of using the OrCam device pediatric individuals with low vision. Assessment of safety will be made by evaluating summary statistics of Adverse events/ Unanticipated problems, Feasibility test, Feasibility questionnaire, and Device use diary in all 30 enrolled participants. We hypothesize that *use of the device will be safe and feasible in pediatric individuals with CLN3*.
- Secondary Endpoint(s): We hypothesize that the *use of OrCam MyEye 2 will enhance the participants' function on visual related tasks as measured by performance on the Function Test, and the Ability and Applicability questionnaires*.

9.2 SAMPLE SIZE DETERMINATION

Since no prior research or data are available and these measures are developed specifically for this pediatric population with multiple disabilities, power calculation is not able to be determined. The study in 12 neurologically intact adults reported a mean improvement of 70% in performance over baseline on the Function Test. We anticipate that the improvement will be lower given the age and comorbidities in the CLN3 cohort, thus propose a total enrolment of 30 pediatric participants. As outlined in **Section 4.2 Scientific Rationale for Study Design**, we anticipate being able to recruit 5 CLN3 and 5 non-CLN3 participants with low vision in one year.

A major purpose of this trial is to obtain pilot data on feasibility and potential functional outcome measures that appears to improve with device use. The pilot data will inform power calculations for a subsequent trial focused on establishing device intervention efficacy.

9.3 POPULATIONS FOR ANALYSES

9.3.1 Evaluable for toxicity

All participants will be evaluable for adverse events from the time of their first use of the OrCam.

9.3.2 Evaluable for objective response

Only those participants who have used the device for at least 3 days and have completed the Feasibility and Efficacy evaluations both before and after device use will be considered evaluable for response.

9.3.3 Evaluable Non-Target Disease Response

Not applicable.

9.4 STATISTICAL ANALYSES

9.4.1 General Approach

For comparisons of before and after device intervention in the same participant and correlation calculations, statistical significance will be determined by corresponding parametric (e.g., paired t-test and Pearson correlation) or non-parametric (Wilcoxon Rank sum test and Spearman correlation) methods. A p value < 0.05 will be considered significant and between 0.05 and 0.10 will be considered a trend. Multiple comparisons will be corrected by appropriate post-hoc analysis.

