4.2 SCIENTIFIC RATIONALE FOR STUDY DESIGN

Currently, there is no device similar to the OrCam available or in accepted use for individuals with CLN3. In addition, there is also no data available on the use of this device in children with low vision. Thus, a combined cohort of pediatric participants with and without CLN3-related disorders will optimize recruitment potential, and provide preliminary information for evaluation of feasibility and efficacy in pediatrics, and specifically in individuals with CLN3-related conditions. To assess efficacy, we will use the study participants' baseline data as controls. This option encompasses the least number of confounding factors for a cohort of small size.

In the CLN3 natural history study (18-CH-0002), accrual rate averages at 8-10 per year. Not all of these individuals will meet the eligibility criteria for this proposed study. However, we anticipate, based on experience with interventional trials of other rare diseases, that families hesitant to participate in an observational study would be more open to participating in an interventional study. Given these considerations, we anticipate an accrual rate of 5 participants per year and a reasonable potential to enroll 20 CLN3 participants over 2-3 years. We have also discussed potential eligible participants with local Ophthalmology groups (Howard University, Johns Hopkins, NEI), and the anticipated number for pediatric individuals with low vision and not CLN3-related condition is estimated to be in the same range. We plan to screen up to 50 participants.

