6 STUDY INTERVENTION

6.1 STUDY INTERVENTIONS(S) ADMINISTRATION

6.1.1 Study Intervention Description

OrCam MyEye 2 is an FDA class 1 device (<https://www.accessdata.fda.gov/scripts/cdrh/cfdocs/cfRL/rl.cfm?lid=397540&lpcd=HPG>). The main components include a 13 megapixels camera, a 3.7V DC (nominal 320mAH) battery, and ancillary charging and glass-mounting supplies. The OrCam MyEye 2 is available in only one size that has dimensions of 76x21x14.9 mm, and weighs 22.5 g. Additional visual and descriptions of the device, its set-up and functions are provided in **Appendices I-K**. The use of the OrCam in this study will be according to the manufacturer's specifications. The device is not intended as an implant and does not present potential for serious risk to the health, safety, or welfare of a subject. Due to its risk profile, the device should be considered a non-significant risk device.

Participants will be trained and asked to use the device for at least 30 minutes daily as indicated in the **Schedules of Activities**. All participants meeting eligibility criteria will enroll in the 1-week study and be exposed to the device use for 5 days. Participants may enter the additional 1-month study if parents/guardians/participants endorse desire to continue using the device at home.

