8.2.1 Clinical Evaluations

1. **Function Test.** The study participants will be asked to complete tasks relating to device-supported daily activities (**Appendix C**). These include identification of printed words (e.g., books, documents, menus, labels, signs) and identification of faces and colors. At Days 1 (baseline) and 5 (1-week evaluation), the Function Test will be done in its entirety via face-to-face encounters. A sub-group of the Function Test items may be done via the use of remote technologies (e.g., videoconferencing). At the 1-month evaluation, if the study participants are able to come to the NIH the Function Test will be done as on Days 1 and 5. If study participants are not able to come for an in-person visit, the sub-group of the Function Test items will be done remotely.
2. **Ability and Applicability Questionnaires.** Parents/Guardians will complete questionnaires of their child's ability to accomplish the tasks in the Function Test without help, and their ratings of how important it would be for their child to accomplish these

tasks without help. (**Appendices D, E**). The questionnaires may be completed using paper or web-based format.

3. **Neuropsychologic Evaluation.** We will assess adaptive behavior using *The Vineland Adaptive Behavior Scales*, Third Edition, Daily Living Scale, based on parent interview. This may be done by methods that do not require in-person meetings (such as via a phone call) to provide adaptability to the protocol and to maximize ability to collect meaningful longitudinal data.
4. **Quality of Life Questionnaires.** Parents/Guardians will complete age-appropriate PedEyeQ[27], PROMIS[28], and Low Vision QOL[29] questionnaires (**Appendices G - I**). The questionnaires may be completed using paper or web-based format.

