9.4.3 Analysis of the Secondary Endpoint(s)

Function Test – Efficacy Scores

Data analysis. Participants' scores will be the sum of items 1 to 7 combining levels a & b and will range from 0 to 14, and the mean duration to complete each task. Analysis will consist of change in scores and mean duration to complete each task from baseline to 1 week and 1 month). No formal statistical tests will be conducted. Interpretation of results will be rule-based.

Rules for data interpretation. Device use is efficacious if at 1-week or 1-month compared to baseline:

- 25% or more of total number of participants increased score by at least 30%
- 25% or more of total number of participants decreased time by at least 30%

Below are some simulations of the power of a paired-sample test for change from baseline, using a sample size of 10 participants. This provides a sense of the possible characteristics of the data and for justifying the sample size.

Simulations for tasks-completed scores

Each simulation study used 1000 replications with $N = 10$. For each replication, baseline and post-baseline sets of scores were randomly generated. Means, standard deviations, and paired-samples t-tests of difference scores (Post-baseline – Baseline)

were computed. Power was computed by the percent of replications (out of 1000) with t-test p-values less than or equal to 0.05. Baselines were generated by randomly selecting, with replication, scores from 0 to 5 with equal probability, 1/6. The baseline range matched the baseline values reported in the adult study. Post-baseline scores included a specified number of baseline cases randomly selected without replacement to improve by 30% (Baseline \times 1.30). Cases with baseline values = 0 were excluded from random selection since percentage change from 0 is undefined.

Simulation 1. Based on the decision rule of 25% of total participants, 3 cases (rounded up since 25% of N= 10 is 2.5) were randomly selected to improve 30% from baseline and the other 7 cases did not improve. *Results: power = proportion of 1000 p-values <= 0.05 = 0.37.*

Simulation 2. 3 cases randomly selected to improve 30% and 7 cases improved by 1 point. *Results: power = proportion of 1000 p-values <= 0.05 = 1.0.*

Simulation 3. 4 cases randomly selected to improve 30% and 6 cases did not improve. *Results: power = proportion of 1000 p-values <= 0.05 = 0.95.*

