Simulation 4. 4 cases randomly selected to improve 30%, 6 cases improved by 1. *Results: power = proportion of 1000 p-values <= 0.05 = 1.0.*

Simulation 5. 2 cases randomly selected to improve 30% and 8 cases did not improve. *Results: power = proportion of 1000 p-values <= 0.05 = 0.00.*

Simulation 6. 2 cases randomly selected to improve 30%, 8 cases improved by 1. *Results: power = proportion of 1000 p-values <= 0.05 = 1.0.*

Simulations with baseline values 1 to 5, # cases improving 30%: 2 to 5; # cases improving by 1: 0 to 3; # cases no improvement: 4 to 8. (For any simulation run, # cases improving 30% + #cases improving by 1 + # cases not improving = 10).

Results: These simulations correct for the problem that percentage improvement is undefined when baseline = 0. When stipulating that percentage improvement is 30% for as few as 2 or 3 cases, power is greater than .99 when only 1 to 3 other randomly selected cases improve by 1 from baseline. Power will be higher if participants' scores improve more than 1 over baseline.

Based on these simulations, a test of efficacy using a paired-samples t-test with N = 10 would be adequately powered provided that post-baseline scores are likely to improve from baseline. Whether or not a sample of 10 is large enough to make conclusions about different characteristics of the sample group is not addressed.

Ability Questionnaire

Data analysis. Proportions of participants with scores 3 or greater in all items from 1-12. No formal statistical tests will be conducted. Interpretation of results will be rule-based.

Rules for data interpretation. Device use is efficacious if there is a 25% increase in the proportion of participants scoring 3 or greater in all items at 1-week or 1-month as compared to baseline.

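### Section 9.4.1 names the Wilcoxon rank sum test, an independent-samples test, for before/after comparisons in the same child; the paired test is the Wilcoxon signed-rank test

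*Combined protocol and SAP*

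**What the plan says.** Section 9.4.1 introduces its methods with the words "For comparisons of before and after device intervention in the same participant" and adds correlation calculations to the same sentence. The methods it then lists are "e.g., paired t-test and Pearson correlation) or non-parametric (Wilcoxon Rank sum test and Spearman correlation) methods". It calls p below 0.05 significant and p from 0.05 to 0.10 a trend, without stating whether tests are one- or two-sided.

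The rest of the plan treats the data as paired:

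- Section 4.2, on efficacy: "we will use the study participants' baseline data as controls".
- Section 9.3.2 counts a child as evaluable for response only with evaluations both before and after device use.
- Section 9.4.3, on sample size: "Below are some simulations of the power of a paired-sample test for change from baseline".

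For the scored endpoints, Sections 9.4.2 and 9.4.3 say "No formal statistical tests will be conducted" and use decision rules instead.

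Two other sets of measures are collected twice. Section 8.2.1 describes the quality of life instruments ("Parents/Guardians will complete age-appropriate PedEyeQ[27], PROMIS[28], and Low Vision QOL[29] questionnaires"), which Section 1.3 schedules on Days 1 and 33. It also describes the Vineland ("Third Edition, Daily Living Scale, based on parent interview"); Section 1.3 schedules the neuropsychologic evaluation at screening and Day 33. No section assigns a test to either.

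**The concern.** The rank sum (Mann-Whitney) test compares two independent groups. Applied to baseline and follow-up scores from the same children, it treats 30 pairs as 60 unrelated children. Its null variance is then too large whenever a child's two scores are positively correlated, as repeated scores on one scale usually are. The paired t-test named beside it does use the pairing, so the two options offered as counterparts answer the question with very different precision.

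At stake is a missed change: a true improvement could be reported as non-significant, or only as a trend. Section 9.2 says a major purpose of this pilot is to find outcome measures that appear to improve, to inform a later trial. The sample is small and the scores are bounded or ordinal, so an analyst could well choose the non-parametric route.

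**Working it through.** **1. Which comparison the sentence covers.** Section 9.4.1 covers within-participant before/after comparisons and correlations, nothing else. The rank sum test could suit the exploratory CLN3 versus non-CLN3 comparison in Section 9.4.9, but neither section assigns it there.

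**2. The plan's own figures.** The nearest stated figures are the powers in Section 9.4.3 for a paired t-test with N = 10. Setup: baseline uniform on 0 to 5, k non-zero cases multiplied by 1.30, the rest unchanged or raised by 1.

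- Simulation 1: stated 0.37; recomputed 0.375 one-sided, 0.00 two-sided.
- Simulation 3: stated 0.95; recomputed 0.966 one-sided, 0.31 two-sided.
- Simulations 2, 4 and 6: stated 1.0; recomputed 1.00.
- Simulation 5: stated 0.00; recomputed 0.00.

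All six reproduce at one-sided 0.05. They are t-test results, so the test name in Section 9.4.1 does not alter them.

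In the setups of Simulations 2, 4 and 6, at two-sided 0.05, the rank sum test has power of about 0.02, against 1.00 for the signed-rank test. These are extreme cases, because every child improves by a nearly fixed amount. In Simulations 1, 3 and 5 neither rank test rejects. Only 2 to 4 differences are non-zero there, and with 4 the smallest one-sided signed-rank p is 1/2⁴ = 0.0625.

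**3. Inputs for a general check.** The maximum of 30 children is from Section 9.2. A smaller set of 20 is assumed, because continuation is voluntary (Section 6.1.1: "Participants may enter the additional 1-month study if parents/guardians/participants endorse desire to continue using the device at home"). Also assumed, because the documents give no value: correlation ρ of 0, 0.3, 0.5 or 0.7, a true shift of 0.5 SD, and two-sided testing at 0.05.

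**4. Type I error by formula.** With no true change, the rank sum statistic's actual variance is about (1 − ρₛ) times the variance the test assumes. For normal scores ρₛ = (6/π)·arcsin(ρ/2). The actual error is about 2·[1 − Φ(1.96/√(1 − ρₛ))]. Simulated values are for n = 30.

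| ρ | ρₛ | 1.96/√(1 − ρₛ) | Formula | Simulated |
|---|---|---|---|---|
| 0 | 0 | 1.96 | 0.050 | 0.047 |
| 0.3 | 0.288 | 2.32 | 0.020 | 0.021 |
| 0.5 | 0.483 | 2.72 | 0.006 | 0.008 |
| 0.7 | 0.683 | 3.48 | 0.0005 | 0.001 |

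**5. Power by formula, n = 30.**

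- Ignoring pairing: the standardised effect is 0.5·√(30/2) = 1.936, and power ≈ Φ((1.936 − 1.96)/√(1 − ρ)), about 0.48 to 0.49 at every ρ.
- Using pairing: the effect is 0.5·√(30/(2(1 − ρ))) = 1.94, 2.31, 2.74, 3.54, and power ≈ Φ(effect − 1.96) = 0.49, 0.64, 0.78, 0.94.

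These normal-theory values run slightly above those simulated for the rank tests.

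**6. Power by simulation (20,000 replications per cell).** Each cell gives rank sum / signed-rank.

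| Scores, n | ρ = 0 | 0.3 | 0.5 | 0.7 |
|---|---|---|---|---|
| Normal, 30 | 0.46 / 0.45 | 0.44 / 0.59 | 0.44 / 0.73 | 0.43 / 0.91 |
| Normal, 20 | 0.32 / 0.31 | 0.29 / 0.42 | 0.27 / 0.55 | 0.24 / 0.77 |
| Five-level ordinal, 30 | 0.43 / 0.42 | 0.42 / 0.54 | 0.42 / 0.67 | 0.40 / 0.84 |
| Lognormal (log SD 0.5), 30 | 0.65 / 0.55 | 0.67 / 0.69 | 0.69 / 0.81 | 0.73 / 0.94 |

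For ordinal and lognormal scores, ρ is set on the underlying normal scale, as is the ordinal shift. At correlation 0 nothing is lost, and with skewed scores the rank sum test is ahead. At 0.3 the loss runs from 0.02 (skewed) to 0.15 (normal, n = 30). From 0.5 upward the loss is clear in every row.

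**The case against.** The strongest reply is that no analysis expressly planned would use this test. Adverse events and diary data are descriptive, the scored primary and secondary endpoints follow decision rules, sub-group analyses follow the same sections, and Section 9.4.9 speaks of summary statistics. Quality of life and Vineland scores are not listed as before/after efficacy endpoints. The Vineland baseline may be up to 6 months old and come from outside records (Section 8.1.2, Table 2). The paired intent is plain elsewhere, so this looks like a slip in naming. The figures rest on a single assumed shift of 0.5 SD, assumed correlations and assumed two-sided testing. The error also makes the test conservative, which is the milder direction in an open-label pilot.

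Most of this stands as a limit on importance. No primary or secondary conclusion changes, and the power losses are illustrations that depend on the assumptions. It does not make the sentence right. The two tests are different procedures, and an analyst who follows Section 9.4.1 as written runs the wrong one. That section also sets the significance and trend thresholds, so it would govern any before/after p-value that is produced.

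**Conclusion.** The concern holds: Section 9.4.1 names an independent-samples test for paired data. The practical reach is narrow, being confined to before/after tests outside the rule-based endpoints, none of which is expressly assigned. Where such a test is run by the non-parametric route, the cost is lost power. At a 0.5 SD shift, correlation 0.5 and n = 30, power falls by 0.29 for normal scores (0.73 to 0.44), 0.25 for five-level ordinal scores (0.67 to 0.42) and 0.12 for skewed scores (0.81 to 0.69). The shift, the correlation and the two-sided level are assumptions, since the documents give none of them. With non-negative correlation the error creates no excess of false positives, and it leaves the estimated change and its variability untouched. It should be corrected, but it does not threaten the trial's main conclusions.

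**What to change.** In Section 9.4.1, replace the Wilcoxon rank sum test with the Wilcoxon signed-rank test as the non-parametric method for before/after comparisons in the same participant. The cost is one wording change. It needs no extra participants, visits or data, and no stated sample size, power figure or decision rule changes.

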9.4.2 Analysis of the Primary Endpoints

Adverse events and Device use diary data will be provided using descriptive statistics.

Feasibility Test

Data analysis. Participants' scores will be the sum of items 1 to 5 and will range from 0 to 5. Analysis will consist of summary descriptive statistics (mean, standard deviation, median, proportion of participants at each score level). No formal statistical tests will be conducted. Interpretation of results will be rule-based.

Rules for data interpretation. Device use is feasible if at baseline, 1-week, or 1-month 50% or more of total number of participants score 3 or greater out of 5.

Feasibility Questionnaire

Data analysis. Participants' scores will be the sum of items 1 to 11 and will range from 0 to 11. Analysis will consist of summary descriptive statistics (mean, standard deviation, median, proportion of participants at each score level). No formal statistical tests will be conducted. Interpretation of results will be rule-based.

Rules for data interpretation. Device use is feasible if at 1-week or 1-month 50% or more of total number of participants score 6 or greater out of 11.

